9.7 Data Protection

Patient confidentiality is strictly held in trust by the participating Investigators, their staff, TRIO or affiliates. This confidentiality is extended to cover testing of biological samples and genetic tests in addition to the clinical information relating to participating patients.

Patient and Investigator personal data which may be included in the study database shall be treated in compliance with all applicable laws and regulations.

When archiving or processing personal data, TRIO shall take all appropriate measures to safeguard and prevent access to this data by any unauthorized third party.

The study protocol, documentation, data and all other information generated will be held in strict confidence. No information concerning the study or the data will be released to any unauthorized third party without prior written approval by TRIO.

The study monitor or TRIO's other authorized representatives will verify documents and records required to be maintained by the Investigator, including but not limited to, medical records (office, clinic or hospital) and pharmacy records for the patients in this study. The clinical study site will permit access to such records.

9.9 Insurance of Liabilities

If required, the Investigator may forward to the IEC/IRB a copy of the insurance document required by TRIO, in order to cover his/her liabilities, and those of any other participating parties.

9.10 Use of Information and Publication

All information concerning the study drug or in connection with this study, supplied by TRIO and/or by any other party collaborating with TRIO within this study, and not previously published, is considered confidential and proprietary information. This information includes, but is not limited to, the IB, clinical protocol, workbooks (if applicable), eCRFs, assay methods, TRIO technical methodology, and basic scientific data. This confidential information shall remain the sole property of TRIO, the respective collaborating party, and shall not be disclosed to others without prior written consent from TRIO. Information shall not be used except in the performance of this study.

To allow for the use of the information derived from this clinical study and to ensure compliance to current regulations, the Investigator is obliged to provide TRIO with complete test results and all data developed in this study. No publication, abstract or presentation of the study will be made without the approval of the SSC. The SSC will review the manuscript to prevent forfeiture of patent rights to data not in the public domain. Prior to publication, the authorship list will be agreed upon by the SSC. For the purpose of analyses, the names on the author list will be given according to the participation in the concept of the study design as well as accrual input (number of eligible patients accrued) by the Investigators at each center. The maximum number of authors will be determined by the publication policy established by the targeted journal. Abstracts and publications will be submitted to the authors and to the SSC at least 30 days prior to the expected date of submission to the intended publisher.

11. APPENDICES

Appendix 1: Eastern Cooperative Oncology Group Performance Status Scale

Grade	Description
0	Fully active, able to carry on all pre-disease performance without restriction.
1	Restricted in physically strenuous activity but ambulatory and able to carry out work of a light and sedentary nature, e.g., light housework, office work.
2	Ambulatory and capable of all self-care, but unable to carry out any work activities. Up and about more than 50% of waking hours.
3	Capable of limited self-care, confined to bed or chair more than 50% of waking hours.
4	Completely disabled. Cannot carry on any self-care. Totally confined to bed or chair.
5	Dead

Appendix 2: Patient Diary Template

See next page. The remainder of this page is intentionally left blank.

Site Staff Instructions

Record the Patient ID.

Minimum duration of treatment with ODM-201 is 14 days, with a recommended maximum duration of 21 days. Treatment must not last more than 35 days.

Record in the below table, the calendar dates (dd/mmm/yyyy, Morning or Evening) corresponding to the initial treatment period with ODM-201 1200 mg per day (Sequence 1).

For grade 1-2 treatment-related AEs only: should any treatment interruption / dose modification take place (to be agreed on with TRIO Medical Monitor), please record in the subsequent row (Sequence 2) the treatment start / stop dates and treatment dose to be taken by the patient. Note: for grade ≥ 3 treatment-related AEs, treatment should be permanently discontinued.

Depending on the day / time when the patient is provided with the ODM-201 bottle, treatment may start with either a Morning or an Evening intake.

The last ODM-201 intake will be on the day prior to breast cancer surgery or before starting neoadjuvant treatment if indicated, in the morning of the Pre-surgery visit (except if the patient is ordered to stop oral intake earlier – please refer to protocol section 6.4.3 “Pre-surgery visit” for guidance).

Please refer to protocol sections 5.3 and 5.4.2 for more details.

Date of ODM-201 bottle dispensation: ____ / ____ / ____

(dd/mmm/yyyy)

Seq.	Treatment Period	Daily Dose	Study Treatment container
1	
From: _____ / _____ / _____ (dd/mmm/yyyy)
 
To: _____ / _____ / _____ (dd/mmm/yyyy)
	
 Morning  Evening
 
 Morning  Evening
 
1200 mg 2 tablets twice a day (with food, at breakfast and dinner)
	
Bottle (containing 140 tablets of ODM-201 300 mg)

2	
From: _____ / _____ / _____ (dd/mmm/yyyy)
 
To: _____ / _____ / _____ (dd/mmm/yyyy)
	
 Morning  Evening
 
 Morning  Evening
 
1200 mg 2 tablets twice a day (with food, at breakfast and dinner)
 
Or
 
 600 mg
 
1 tablet twice a day (with food, at breakfast and dinner)
	

Date of Pre-surgery visit: ____ / ____ / ____

–

(dd/mmm/yyyy)

Date of surgery: ____ / ____ / ____

(dd/mmm/yyyy)

Patient Instructions:

- **Swallow the ODM-201 whole tablets with water and do not chew them prior to swallowing.**
- **Take the tablets together with food if possible at approximately the same time twice a day (for example, with breakfast and dinner each day).**
- **Your study doctor may decide to reduce or hold your study treatment. Please follow his/her instructions carefully.**
- **If you miss an intake or vomit following ODM-201 intake, you should skip the missed/vomited intake and you should take the next one as scheduled. You should not make it up.**
- **If you inadvertently take more than the required number of tablets at a given intake, please take your next intake as scheduled. Please report this on your patient diary and inform your study doctor immediately.**
- **If a tablet is broken or damaged, the tablet should not be used. Inform your study doctor or nurse.**
- **If you lose a tablet accidentally (e.g. tablet drops in the sink, falls on the ground etc), please report it on your patient diary (in the section “Other comments”) and inform your study doctor or nurse.**
- **Keep the tablets in the bottle provided and do not transfer them to any other container.**
- **Record the number of tablets taken at each intake in the diary section below.**
- **To prevent any dosage error, you should complete your diary prior to taking the study treatment to ensure you will take the correct number of tablets.**
- **ALWAYS bring back the bottle and your completed diary to the clinic at each visit (treatment visit if any and Pre-surgery visit).**
- **In case of any question or problem please contact :**
 - **Name of study site staff: _____**
 - **Phone #:_____**

Patient Diary

DAY	DATE (dd/mmm/yyyy)	INTAKE	TIME Hour/Min (24:00 clock)	Number of tablets TAKEN	COMMENTS
Example: Day X	Example: 15/DEC/2016	Morning intake	8:00	2	
		Evening intake	19:00	1	Only 1 tab taken, the other one was missed in error
Day 1		Morning intake			
		Evening intake			
Day 2		Morning intake			
		Evening intake			
Day 3		Morning intake			
		Evening intake			
Day 4		Morning intake			
		Evening intake			
Day 5		Morning intake			
		Evening intake			
Day 6		Morning intake			
		Evening intake			
Day 7		Morning intake			
		Evening intake			
Day 8		Morning intake			
		Evening intake			
Day 9		Morning intake			
		Evening intake			
Day 10		Morning intake			
		Evening intake			
Day 11		Morning intake			
		Evening intake			
Day 12		Morning intake			
		Evening intake			

DAY	DATE (dd/mmm/yyyy)	INTAKE	TIME Hour/Min (24:00 clock)	Number of tablets TAKEN	COMMENTS
				Report in the cells below the number of tablets taken (e.g. 2, 1 or 0) at each intake.	Please use this section to write down any side effects you are experiencing on a given day, explanation for any extra tablet taken or missed tablet, etc.
Day 13		Morning intake			
		Evening intake			
Day 14		Morning intake			
		Evening intake			
Day 15		Morning intake			
		Evening intake			
Day 16		Morning intake			
		Evening intake			
Day 17		Morning intake			
		Evening intake			
Day 18		Morning intake			
		Evening intake			
Day 19		Morning intake			
		Evening intake			
Day 20		Morning intake			
		Evening intake			
Day 21		Morning intake			
		Evening intake			
Day __		Morning intake			
		Evening intake			
Day __		Morning intake			
		Evening intake			
Day __		Morning intake			
		Evening intake			
Day __		Morning intake			
		Evening intake			
Day __		Morning intake			
		Evening intake			

DAY	DATE (dd/mmm/yyyy)	INTAKE	TIME Hour/Min (24:00 clock)	Number of tablets TAKEN	COMMENTS
				Report in the cells below the number of tablets taken (e.g. 2, 1 or 0) at each intake.	Please use this section to write down any side effects you are experiencing on a given day, explanation for any extra tablet taken or missed tablet, etc.
Day __		Morning intake			
		Evening intake			
Day __		Morning intake			
		Evening intake			
Day __		Morning intake			
		Evening intake			
Day __		Morning intake			
		Evening intake			
Day __		Morning intake			
		Evening intake			
Day __		Morning intake			
		Evening intake			
Day __		Morning intake			
		Evening intake			
Day __		Morning intake			
		Evening intake			
Day __		Morning intake			
		Evening intake			
Day __		Morning intake			
		Evening intake			
Day __		Morning intake			
		Evening intake			

Other comments (e.g.: lost or damaged tablets):

Signature Manifest

Document Number: TRIO030-MLD-0001

Revision: 03

Title: Clinical Trial Protocol

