1.3.2 Rationale for Regimen and Dose Selection

In TRIO030, darolutamide will be given at a dose of 600 mg (2 × 300 mg tablets) b.i.d. to a daily dose of 1,200 mg. Darolutamide should be taken with food since exposure and C_{max} are reduced in fasting conditions.

Darolutamide has been studied in doses ranging from 100 mg to 900 mg b.i.d. in a phase I dose escalation and dose finding study. No dose-limiting toxicities were observed in this study and the maximum tolerated dose was not reached. Systemic exposure to darolutamide increased dose-proportionally in the dosing range from 100 to 700 mg b.i.d. At 900 mg b.i.d. dose there was no further increase in C_{max} or AUC observed when compared to 700 mg b.i.d. Based on the results of this phase I study, the recommended dose was 600 mg b.i.d. for further development. At the dose of 600 mg b.i.d. most AEs were grade 1-2 and assessed by the Investigators as not related to protocol treatment.

Therefore, the dose selected in the study is considered as safe and is the dose that is being used in current darolutamide trials in patients with other primary cancer sites.

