- The first day of darolutamide administration in the study is considered Day 1. On or prior to Day 1 the patient will be provided with a bottle with 140 tablets containing 300 mg of darolutamide each (enough for 35 days of treatment at a daily dose of 1,200 mg). Patient will be instructed that the last protocol treatment intake should be the one in the morning of the Pre-surgery visit. The last darolutamide intake will be on the day prior to BC surgery, or the day before pre-NAST biopsy when the Pre-surgery visit should occur. Exceptions to this rule are when patient is ordered to stop oral intake before the day prior to BC surgery/pre-NAST biopsy, when BC surgery/pre-NAST biopsy is planned for a Monday or the day following a holiday, or in case that performing Pre-surgery visit on the same day of BC surgery/pre-NAST biopsy is required by site due to logistical reasons or patient's/physician's convenience (refer to section 6.4.3 for guidance).

Darolutamide should be taken approximately at the same time each day, twice a day. It is recommended that darolutamide be taken with food; recommendation is to take it with breakfast and dinner each day. Patients will ingest darolutamide whole tablets with water. No tablet should be ingested if it is broken, cracked, or otherwise not intact.

If the patient misses an intake or vomits following darolutamide administration, the missed/vomited dose should be skipped and the patient should take the next intake when scheduled. No “make-up dose” or increased dosing should occur.

If a patient accidentally or intentionally takes a higher daily dose than the one recommended per protocol and up to 1,800 mg (i.e. up to 6 × 300 mg tablets), protocol treatment should continue as scheduled without any dose reduction or skip. For example, if by mistake the patient takes 4 tablets in the first daily intake she can still take 2 tablets in the second daily intake since a total daily dose of 1,800 mg is not exceeded. The Medical Monitor should be contacted for any dose taken that exceeds 1,800 mg daily.

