7.4 Management of Specific Cases

7.4.1 Medication Errors

In the event of a medication error, the patient should be observed closely for signs of toxicity. Medication errors include the accidental or intentional use of darolutamide in a daily dose greater than the protocol-specified daily dose. Appropriate supportive treatment should be provided if clinically indicated. In case of toxicity derived from the medication error, dose modification recommendations from section 5.4.2 should be followed.

The highest darolutamide dose administered in clinical trials is 1,800 mg daily, with no maximum tolerated dose achieved and no dose-limiting toxicity experienced by patients.

If an AE is associated with (“results from”) a medication error, the corresponding AE should be reported as SAE, even if no other seriousness criteria are met.

In cases of a medication error without any associated AE, the medication error should be reported as a non-serious AE, using terminology like “accidental or intentional overdose without adverse effect”, “medication error without adverse effect” or similar.

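### The patient diary's overdose instruction omits the protocol's 1,800 mg daily limit, so following it after a first intake of 5 or 6 tablets takes the day to 2,100 or 2,400 mg

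*Protocol*

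**What the plan says.** Protocol section 5.3.2.1 covers a patient who "takes a higher daily dose than the one recommended per protocol and up to 1,800 mg": she continues as scheduled, with no dose reduced or skipped. It expresses the limit as 6 tablets of 300 mg. Its example is a first intake of 4 tablets instead of 2, after which "she can still take 2 tablets in the second daily intake since a total daily dose of 1,800 mg is not exceeded". For larger amounts the section adds: "The Medical Monitor should be contacted for any dose taken that exceeds 1,800 mg daily".

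The Patient Instructions in Appendix 2 tell the patient: "If you inadvertently take more than the required number of tablets at a given intake, please take your next intake as scheduled". The next sentence reads: "Please report this on your patient diary and inform your study doctor immediately". Another bullet asks her to follow the study doctor's instructions if treatment is reduced or held. No patient bullet mentions 6 tablets or 1,800 mg.

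Section 7.4.1 states: "The highest darolutamide dose administered in clinical trials is 1,800 mg daily". On the dose-escalation study, section 1.3.2 reports: "No dose-limiting toxicities were observed in this study and the maximum tolerated dose was not reached".

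**The concern.** The diary keeps the protocol's action and drops its condition. In section 5.3.2.1 the daily total is the reason the second intake is allowed; in the diary the second intake follows an excess of any size. For some errors it is then the trial's own instruction, and not the error alone, that takes the patient past the highest daily dose the protocol says has been given in trials.

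The diary matters because dosing is at home from a bottle of 140 tablets. When treatment lasts 14 to 21 days, only the Pre-surgery visit is required after Day 1 unless another is clinically indicated (section 6.4.2). The protocol expects no direct benefit to the patient from the drug (section 1.3.1), so nothing offsets avoidable excess dosing.

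**Working it through.** **Inputs.** Tablet strength 300 mg; full dose 2 tablets twice daily; limit on continuing as scheduled 1,800 mg a day (all section 5.3.2.1). Reduced dose 300 mg, that is 1 tablet, twice daily (section 5.4.2 and the diary's second treatment sequence).

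**Formula.** Day's total = (tablets at first intake + scheduled tablets at second intake) × 300 mg.

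**The protocol's own figure.** 6 × 300 = 1,800 mg, and the example gives (4 + 2) × 300 = 1,800 mg. Both reproduce exactly.

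**Error at the first intake, full dose:**

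| First intake (tablets) | Error alone | After the diary-directed 2 tablets | Against 1,800 mg |
|---|---|---|---|
| 3 | 900 mg | 1,500 mg | within |
| 4 | 1,200 mg | 1,800 mg | at the limit |
| 5 | 1,500 mg | 2,100 mg | 2,100/1,800 = 1.167, 17% above |
| 6 | 1,800 mg | 2,400 mg | 2,400/1,800 = 1.333, 33% above |
| 7 | 2,100 mg | 2,700 mg | already above before the next intake |

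**Error at the first intake, reduced dose.** 5 then 1 gives 6 × 300 = 1,800 mg, at the limit. 6 then 1 gives 7 × 300 = 2,100 mg, 17% above. With 7 or more the error has already passed the limit.

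The diary-directed intake is therefore what crosses the limit in exactly these cases: a first intake of 5 or 6 tablets at full dose, or of 6 at reduced dose.

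**Error at the evening intake.** The next intake falls on the following day, so the diary does not change the total for the day of the error. For example, 2 tablets in the morning and 6 in the evening is already 8 × 300 = 2,400 mg through the error alone.

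**The case against.** The strongest reply is that the safeguard sits in the same bullet. The patient must inform the study doctor immediately, and the diary has a line for a site telephone number. Intakes are at breakfast and dinner; the diary's example times of 8:00 and 19:00 are 11 hours apart. The staff page of the diary refers to protocol section 5.3, so whoever takes the call has the limit to hand. This stands as a strong mitigation: in most cases the call will come before the next intake. It does not remove the mismatch, because the intake is not made to wait for the doctor's answer. A patient who cannot reach the site and follows the diary takes the tablets.

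Second, section 5.3.2.1 never orders an intake to be withheld above 1,800 mg, and its Medical Monitor sentence is worded for a dose already taken. That is correct. The protocol stops endorsing continuation above the limit without saying what to do before the next intake. The diary fills that gap with an instruction to continue, and the sentence proposed for section 5.3.2.1 would be a new rule.

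Third, the likely harm is small. No dose-limiting toxicity was seen, and section 1.3.2 reports no further rise in peak concentration or AUC at 900 mg twice daily compared with 700 mg twice daily. A single intake of 5 or 6 tablets is a larger departure from the schedule than the ordinary 600 mg that follows. All of this limits the size of the point. The documents nevertheless report no experience above 1,800 mg daily.

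Fourth, the SAP (section 2.3) gives enrollment closure as 14 February 2019. Allowing 5 days to start treatment and 35 days of dosing, compliant dosing ended by about 25 March 2019. The correction now serves re-use of the template; the closed enrollment does not make the text right.

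**Conclusion.** The concern holds as a minor safety correction. The diary directs continuation beyond the limit on which section 5.3.2.1 bases it. The excess is 300 mg (17%) after a first intake of 5 tablets and 600 mg (33%) after 6 at full dose, and 300 mg (17%) after 6 at reduced dose.

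These figures assume that the error is at the first intake of the day and that the patient takes the next intake before any contrary advice. The documents give no frequency for such errors. The patient also holds a copy of the signed consent form, which was not available for this review, so nothing is concluded about what it says. Endpoints, analysis populations and analyses are unaffected.

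**What to change.** Reword the diary bullet so that the patient takes the next intake as scheduled only if her total for that day will not exceed 6 tablets; if it would, she takes no further intake that day until she has spoken to her study doctor. Keep the present instruction to record the error and inform the doctor immediately.

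Add one sentence to section 5.3.2.1: the site contacts the Medical Monitor before any further intake that would bring the day's total above 1,800 mg.

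A daily total does not catch an evening error followed by the next morning's intake. If the sponsor wants that covered, one more clause would do it: after 5 or more tablets at any one intake, call the study doctor before the next.

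The cost is one diary bullet, one protocol sentence and re-issue of the diary template. Visits, data collection and analysis do not change.

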|---|----|
| 3.5.6. Death..... | 12 |
| 4. List of Planned Statistical Outputs | 12 |
| 4.1. Planned Tables..... | 12 |
| 4.2. Planned Listings..... | 14 |
| 4.3. Planned Graphs..... | 16 |
| 5. Appendix | 16 |
| 5.1. Protocol Synopsis – Protocol v3.0..... | 16 |
| 5.2. Protocol Synopsis – Protocol v5.0 (Germany)..... | 22 |

List of Abbreviations

| | |
|--------|--|
| ADSL | Subject-Level Analysis Dataset |
| ADaM | Analysis Data Model |
| AE | Adverse Events |
| CM | Concomitant Medications |
| CTCAE | Common Terminology Criteria for Adverse Events |
| EBC | Early Breast Cancer |
| EoS | End of Study |
| ITT | Intent-to-treat or Intention-to-treat |
| ITTF | Intent-to-treat Population Flag |
| MedDRA | Medical Dictionary for Regulatory Activities |
| NCI | National Cancer Institute |
| PT | Preferred Term |
| Q1 | First Quartile |
| Q3 | Third Quartile |
| RDI | Relative Dose Intensity |
| SAE | Serious Adverse Event |
| SAFF | Safety Population Flag |
| SAP | Statistical Analysis Plan |
| SAS® | Statistical Analysis System Software |
| SOC | System Organ Class |
| SSC | Study Steering Committee |
| TEAE | Treatment Emergent Adverse Event |
| TRIO | Translational Research in Oncology |
| WHODD | World Health Organization Drug Dictionary |

1. Introduction

This Statistical Analysis Plan (SAP) describes the detailed statistical methodology for executing the statistical analyses of the Secondary Objective according to TRIO030 protocol version 3.0 and version 5.0 (Germany).

Statistical analysis will be performed by TRIO using SAS® software Version 9.4 or higher.

2. Study Design and Objectives

2.1. Study Design

The protocol synopsis is provided in Appendix 5.1 and Appendix 5.2. Refer to the protocol for additional details.

2.2. Study Objectives

2.2.1. Primary Objective

The primary objective for this study is to identify the molecular alterations that occur in human Breast Cancer (BC) tissue, following short-term exposure to darolutamide (ODM-201) in female subjects with Early Breast Cancer (EBC).

